##### D.2. Study population

Patients with the first episode of acute pancreatitis

##### D.3. Study design

This project will take place in 4 distinct phases:

Phase 1: Recruitment of patients with acute pancreatitis and stratification of them according to the severity of acute pancreatitis and development of EPI (12-month follow-up).

All patients admitted to the Gastroenterology Department of Coimbra Hospital and University Centre by the first episode of acute pancreatitis will be included, consecutively, according to the revised Atlanta criteria 2012 and taking into account the inclusion/exclusion criteria and the minimum number of patients needed to obtain statistical power.

Inclusion criteria: Definitive diagnosis of acute pancreatitis, according to revised Atlanta criteria 2012.4

Exclusion criteria: Age <18years; History of allergy, hypersensitivity or contraindication to use of PERT; Prior acute pancreatitis; Other causes that may occur with EPI, including celiac disease, diabetic gastroparesis, chronic pancreatitis, cystic fibrosis, pancreatic neoplasia, ampuloma, somatostatinoma, somatostatin analog therapy, small bowel pathology, inflammatory bowel disease, and rare diseases associated with exocrine pancreatic insufficiency (Zollinger-Ellison syndrome, Shwachman-Diamond syndrome, Johanson-Blizzard syndrome); Prior gastrointestinal or pancreatic surgery or endoscopic/surgical therapy for obesity; medication with orlistat or acarbose; Respiratory pathology (severe chronic obstructive pulmonary disease), hepatic (Child-Pugh C cirrhosis) or biliary (obstructive jaundice) severe pathology; Non-compliance for PERT (when indicated); Uncontrolled thyroid pathology; Refusal/incapacity to give informed consent; and Follow-up period <12months after acute pancreatitis diagnosis.

Sample size calculation: For an estimated prevalence of EPI in the adult population of 25% and a drop-out rate of 10%, it was determined that for a 95% confidence level and 10% sampling error, it will be necessary to include 42 patients in each of the therapeutic arms (PERT vs placebo), making a total of 84 patients.

Diagnosis of EPI and stratification of patients: See Task 1.

Phase 2: Double-blind randomized placebo-controlled trial for patients with EPI after acute pancreatitis for PERT and collection of stool and blood samples before and after

PERT/placebo (6 months post-randomization).

Randomization of patients with EPI following acute pancreatitis for PERT vs placebo. The efficacy, safety and compliance of PERT will be evaluated at 1 (for adjusting PERT dose) and 6 months after PERT start.

Phase 3: Analysis of gut microbiota and assessment of quality of life, and the impact of PERT on clinical and nutritional course, gut dysbiosis and patients' quality of life (at the diagnosis of acute pancreatitis, EPI and after PERT). Evaluation of richness, diversity and uniformity of gut microbiota by DNA sequencing

using the hypervariable region of the 16S rRNA gene. Assessment of quality of life using validated Portuguese versions of SF-36 and QLC-C30-V.3 Assess of PERT impact on clinical and nutritional course, gut dysbiosis and patients' quality of life.

Phase 4: Analysis of immunological changes and the impact of PERT on clinical and nutritional course and immunological status (at the diagnosis of acute pancreatitis, EPI and after PERT). Evaluation of immunological changes through the study of cell populations by flow cytometry (CD4+, CD8+, B-cell, T-cell, natural killer cells, cells ratio) and cytokines, chemokines and growth factors by xMAP/Luminex. Assess PERT impact on clinical and nutritional course and immunological changes.

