### **Abstract**

**Introduction:** Acute pancreatitis represents an acute inflammatory process of the pancreas, which undergoes local and systemic complications, associated with non-negligible morbidity and mortality, and significant economic and quality of life impact. Even after the recovery phase, the development and persistence of sequelae from the inflammatory/necrotic process, including exocrine and endocrine pancreatic insufficiencies, are frequent. Although well documented as consequence of other pancreatic conditions, exocrine pancreatic insufficiency (EPI) after acute pancreatitis is poorly studied and probably underdiagnosed. The prevalence, diagnosis, independent risk factors and therapeutic approaches for EPI after acute pancreatitis need further investigation. Recent evidence suggests the involvement of the pancreas-intestinal axis and immunological dysfunction in several pancreatic pathologies, although their role in the development of EPI after acute pancreatitis is still scarce. Pancreatic enzyme replacement therapy (PERT) is the only treatment currently available in EPI, but the timing for start and duration of this therapy in acute pancreatitis remain to be established.

**Objectives:** Primary objectives: To determine the prevalence, clinical, analytical and nutritional biomarkers and duration of EPI after acute pancreatitis, as well as changes in gut microbiota and immunologic response, and quality of life in EPI and response to PERT after acute pancreatitis. Secondary objectives: To determine the prevalence and biomarkers associated with endocrine pancreatic insufficiency following acute pancreatitis and the presence of gut dysbiosis and immunologic changes in acute pancreatitis according to its severity.

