**Methods:** Prospective longitudinal study of total of patients consecutively admitted to the gastroenterology Department of Coimbra Hospital and University Centre with acute pancreatitis diagnosis and double-blind randomized placebo-controlled clinical trial of PERT in patients developing EPI after acute pancreatitis. This study will be conducted in 4 Phases: Phase 1 - Recruitment of patients with acute pancreatitis and stratification of them according to the severity of acute pancreatitis and development of EPI (12-month follow-up), diagnosed by fecal elastase-1, C-labeled mixed triglyceride breath test assessing exocrine pancreatic function and comparison of them with 72-hour fecal fat quantification, as gold standard; Phase 2 – Double-blind randomized placebo-controlled trial in patients with EPI after acute pancreatitis for PERT with assessment of efficacy and safety of this therapy at 1 and 6 months post-randomization; Phase 3 - Evaluation of richness, diversity and uniformity of gut microbiota by DNA sequencing using the hypervariable region of the 16S ribosomal RNA gene as a taxonomic identification marker and assessment of quality of life using SF-36 and QLC-C30-V.3 scales (validated versions for the Portuguese population) in EPI patients after acute pancreatitis, and the impact of PERT on clinical course, gut dysbiosis and quality of life of patients (at the diagnosis of acute pancreatitis, EPI and after PERT); and Phase 4 – Analysis of immunological changes through the study of cell populations by flow cytometry (CD4+, CD8+, B-cell, T-cell, natural killer cells, cells ratio) and cytokines, chemokines and growth factors by xMAP/Luminex, at the diagnosis of acute pancreatitis, EPI and after PERT.

**Expected results, impact and scientific outputs:** Data on the prevalence of EPI after acute pancreatitis in its different forms of severity and the role of gut dysbiosis and immunologic changes remains unclear. It's expected that an adequate and timely diagnosis of this clinical condition will allow an early start of therapy with positive impact on clinical course, immunologic and gut homeostasis, survival and quality of life. With this study we expect to obtain a prevalence of EPI at admission of 25-62%, which should decrease during

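### Read literally, the exclusion for less than 12 months of follow-up removes enrolled patients for what happens after enrolment, so EPI results before month 12 would describe completers only

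*Combined protocol and SAP*

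**What the plan says.** The design is a prospective, single-centre longitudinal study (D.1). In D.3, Phase 1, patients admitted "by the first episode of acute pancreatitis will be included, consecutively", with 12 months of follow-up planned. The exclusion list in the same section ends with "Follow-up period <12months after acute pancreatitis diagnosis". It has no qualifier such as expected or anticipated.

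Other places that bear on the point:

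- **B. Objectives.** Prevalence and duration of EPI, and its biomarkers, form the first primary objective.
- **Abstract, expected results.** "With this study we expect to obtain a prevalence of EPI at admission of 25-62%, which should decrease during" follow-up. Some patients are therefore expected to have EPI from the start.
- **D.3, sample size.** "For an estimated prevalence of EPI in the adult population of 25% and a drop-out rate of 10" per cent, and "for a 95% confidence level and 10% sampling error", the plan concludes that "it will be necessary to include 42 patients in each of the therapeutic arms (PERT vs placebo), making a total of 84 patients".
- **D.4.** Kaplan-Meier curves are planned for EPI over time, and Cox regression for factors associated with EPI. A per-protocol rule that drops losses to follow-up and non-compliers is stated for PERT efficacy only. No analysis set is stated for Phase 1.
- **D.3, Phase 1.** "Diagnosis of EPI and stratification of patients: See Task 1". That task is not in the supplied text.

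**The concern.** An eligibility criterion should be decidable when the patient is enrolled. Length of follow-up achieved is not: in a prospective cohort it becomes known only when the patient reaches month 12 or fails to. Followed as written, the criterion deletes patients afterwards because they died, withdrew or were lost, and their EPI data go with them.

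The estimates that use data from before month 12 would then apply only to people who survived and stayed for a year. They are biased if leaving is related to EPI. That is plausible here. The Abstract describes acute pancreatitis as "associated with non-negligible morbidity and mortality" and expects severity and necrosis to go with EPI. For duration, a patient who dies with EPI still present disappears instead of counting as unresolved at last contact. A bias of this kind does not shrink as more patients are recruited.

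In the trial, data from patients already randomised, including safety data, could be lost by the same route.

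**Working it through.** **1. The plan's own figure.** The sample size is not in dispute. It is reproduced to show what the 10% figures refer to. A single-proportion precision formula gives n = 1.96² × 0.25 × 0.75 / 0.10² = 72.03, rounded up to 73. Half of that, rounded up, is 37 per arm; 37 / 0.90 = 41.1, rounded up to 42 per arm, or 84 in total. This matches. The 10% drop-out therefore belongs to the 84 trial patients. The plan gives no mortality or attrition rate for the Phase 1 cohort.

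**2. Which estimates the criterion changes.**

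- *Admission and visits before month 12:* changed, because patients with a result are removed if they later leave.
- *Month 12, among those assessed:* unchanged. A patient who left earlier has no month-12 result to remove.
- *Time to EPI, duration of EPI, Cox model:* changed. Every retained patient has at least 12 months of follow-up, so nobody is left to censor before month 12.

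**3. Illustration for a visit before month 12.** Let p be EPI prevalence among completers, r the share removed and q the prevalence among those removed. Full-cohort prevalence = p(1 − r) + rq. Take p = 25% (the plan's sample-size value).

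| r | q = 0 | q = 12.5% (half of p) | q = 50% (twice p) | q = 100% |
|---|---|---|---|---|
| 10% (trial drop-out, assumed to apply to the cohort) | 22.5% | 23.8% | 27.5% | 32.5% |
| 20% (assumed) | 20.0% | 22.5% | 30.0% | 40.0% |

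Seen from the other side, suppose the true cohort prevalence is 25%. Completers would show (0.25 − rq)/(1 − r). With r = 10% this is 26.7%, 23.3% or 20.9% for q = 10%, 40% or 62%. With r = 20% it is 28.8%, 21.3% or 15.8%. The shift is zero only when q = p.

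**4. The trial.** Visits fall 1 and 6 months after PERT start (D.3, Phase 2), and the supplied text does not fix when after diagnosis randomisation occurs. Two examples, taking treatment to start at randomisation:

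- Randomised at month 3, 6-month visit at month 9, lost at month 10: follow-up is under 12 months, so the patient is removed although the trial visits are complete.
- Randomised at month 7, 1-month visit at month 8, lost at month 9: also under 12 months, so removed with the safety data collected.

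Exposure therefore does not depend on the month of randomisation, provided that follow-up ends before month 12 after diagnosis. The per-protocol rule in D.4 does not make this moot, because it concerns efficacy only.

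**The case against.** The strongest reply is that the criterion means expected availability, judged at enrolment. Several things support this. It sits in an eligibility list. The plan allows for drop-out. D.4 has its own rule for losses, which would be largely redundant if early losses were already excluded. Kaplan-Meier and Cox methods are natural choices only if partial follow-up is kept. The supplied text is also incomplete: Task 1 is absent, and the reference list runs to 29 while the citations stop at 25. The missing sections might settle the matter.

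This stands as a reason for caution but does not resolve the wording. The criterion carries no qualifier. The drop-out allowance fits either reading, since one can inflate enrolment in order to end with enough completers. Placement in the list is weak evidence, because the same list excludes patients who do not comply with PERT when it is indicated, a condition ordinarily seen only after EPI is found and treatment begins. No supplied section keeps early deaths and losses in the Phase 1 analysis.

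Two further objections are right and limit the point. The criterion does not alter month-12 prevalence among those assessed. And whether deaths belong in the denominator for resolution of EPI is a choice of estimand, so a competing-event analysis is optional.

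**Conclusion.** The point holds conditionally. As worded, the criterion permits removal of enrolled patients for a post-enrolment event, and two analysts could take different cohorts from the same text. Under the literal reading, EPI prevalence before month 12, time to EPI, duration and the risk-factor analysis are conditioned on completing a year, and randomised patients can be lost from safety reporting.

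Direction and size cannot be derived from the documents. The bounds of 22.5–32.5% (10% removed) and 20–40% (20% removed) rest on assumed removal rates and on 25% EPI among completers. That EPI results exist from admission is inferred from the expected-results text; no testing schedule is in the supplied sections.

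A reader might infer more than this, and the documents do not support it:

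- *That EPI will be underestimated because severe cases die.* Losses of mild, recovered patients would push the other way, and no rates are given.
- *That every prevalence estimate is distorted.* Month-12 prevalence among those assessed is not changed by the criterion.
- *That the sponsor intends to discard early deaths.* The benign reading remains open.

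Nor do the documents show that the effect is small. The 10% sampling error comes from a calculation needing 73 evaluable patients. If 84 EPI patients are to be found at 25% prevalence and all are randomised, the cohort is 84 / 0.25 = 336, with a 95% half-width of 1.96 × √(0.25 × 0.75 / 336) = 4.6 points. The upper extreme at 10% removed (+7.5 points) exceeds that.

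**What to change.** In D.3:

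- Delete the criterion, or reword it to exclude patients not expected to be available for 12 months of follow-up, judged at enrolment.
- State that every eligible consenting patient stays in the Phase 1 cohort.
- State that this criterion does not remove randomised patients from the trial or from its safety reporting.
- State whether the exclusion for PERT non-compliance is judged at enrolment, so that it does not take EPI patients out of the Phase 1 cohort later.

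In D.4:

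- Report admission prevalence in all patients tested, and later prevalence with the number assessed at each visit.
- Censor losses at last contact in the planned Kaplan-Meier and Cox analyses.
- Report deaths before month 12 separately by EPI status. A competing-event analysis may be added.

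The cost is the rewording in D.3 and a few sentences in D.4. No visits or tests are added. The downside is slightly more analysis work and some incomplete follow-up to report. If Task 1 already defines the Phase 1 analysis set, a cross-reference to it may be enough for that item.

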### **B. Objectives**

#### Primary objectives

- To determine the prevalence and duration of EPI following acute pancreatitis, and analytical and nutritional biomarkers related to the development of this complication;
- To evaluate when to start, the efficacy, safety and the duration of PERT in patients with EPI following acute pancreatitis;
- To assess changes in gut microbiota in EPI following acute pancreatitis and response to PERT;
- To assess changes in immunologic response in EPI following acute pancreatitis and response to PERT;
- To assess quality of life in EPI following acute pancreatitis and response to PERT.

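### The 42 patients per arm for PERT versus placebo are justified by a calculation for estimating one prevalence, which gives no basis for the treatment comparison

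*Combined protocol and SAP*

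**What the plan says.** All references are to the combined protocol and SAP.

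- **Section D.3, Phase 1, sample size calculation.** The inputs are "For an estimated prevalence of EPI in the adult population of 25% and a drop-out rate of 10" per cent, and the target is "for a 95% confidence level and 10% sampling error". The conclusion is that "it will be necessary to include 42 patients in each of the therapeutic arms (PERT vs placebo), making a total of 84 patients". No formula is named.
- **Same section, recruitment text.** Consecutive inclusion is to take account of "the minimum number of patients needed to obtain statistical power", but no power value follows.
- **Section B, primary objectives.** One is "To determine the prevalence and duration of EPI following acute pancreatitis". Another covers the efficacy, safety, timing and duration of PERT.
- **Section D.2.** The study population is "Patients with the first episode of acute pancreatitis".
- **Section D.3, Phase 2.** The trial step is "Randomization of patients with EPI following acute pancreatitis for PERT vs placebo", with efficacy, safety and compliance looked at 1 and 6 months after the start of PERT.
- **Section D.4.** Significance is p < 0.05, with sidedness not stated. PERT efficacy is analysed per protocol, leaving out patients lost to follow-up and those not compliant with PERT.
- **Material not supplied.** Phase 1 adds "Diagnosis of EPI and stratification of patients: See Task 1", and Task 1 is not in the text available for review. The abstract has a gap where the total number of patients would stand.

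**The concern.** The paragraph states a number per treatment arm, but every input describes how precisely a single proportion would be estimated. None describes a difference between PERT and placebo. The two questions also concern different patients. Prevalence needs a denominator of acute pancreatitis patients with and without EPI, whereas the randomised patients have EPI by definition and so carry no information on how common it is.

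PERT efficacy is a primary objective. As written, the paragraph gives the impression that the arms were sized for that objective, yet a reader cannot tell what difference the trial could detect or on which endpoint. Nor can the reader tell whether 84 is the number to randomise or the number to recruit with pancreatitis. The two readings lead to very different trials and to very different recruitment demands on one centre.

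**Working it through.** **1. Reproducing the plan's figure.** Inputs from section D.3: p = 0.25, half-width d = 0.10 (sampling error read as absolute percentage points), 95% confidence, 10% drop-out. Formula: n = z² p(1 − p)/d², divided by (1 − 0.10).

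- z = 2: 4 × 0.25 × 0.75/0.01 = 75; 75/0.9 = 83.3, rounded up to 84 = 2 × 42.
- z = 1.96: 72.03; 72.03/0.9 = 80.03, rounded up to 81. Rounding to 73 first gives 73/0.9 = 81.1, rounded up to 82.

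The total is thus recovered as one prevalence sample split in two. The route is inferred, since the plan names no formula. The conclusion does not depend on z: no value of z turns these inputs into a two-group comparison.

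**2. Reading A: 84 patients with EPI are randomised.** Evaluable per arm: 42 × 0.9 = 37.8, taken as 38. Two-sided 0.05 and 80% power are assumptions.

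| Quantity, 38 per arm | Result |
|---|---|
| Detectable difference, two-sample t-test | 0.65 SD |
| Power for 0.5 SD | 58% |
| Power for 50% vs 80% | 79.5% |
| Power for 50% vs 70% | 43% |
| Expected 95% CI half-width, means: t(0.975; 74) × √(2/38) | 0.46 SD |
| Expected 95% CI half-width, proportions near 50%: 1.96 × √(2 × 0.25/38) | about 22 points |

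The per-protocol exclusion of non-compliers in section D.4 reduces these numbers further, at a rate the plan does not give. If a further 10% to 20% are excluded (assumption), 38 × 0.9 = 34 or 38 × 0.8 = 30 per arm remain, and the detectable difference rises to 0.69 or 0.74 SD.

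Acute pancreatitis patients needed to yield 84 with EPI, before losses and refusals:

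- at the 25% used in the paragraph: 84/0.25 = 336;
- at the 26.5% quoted in the literature review for follow-up under 12 months: 84/0.265 = 317;
- at the 20% lower bound in the literature review: 84/0.20 = 420.

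With 336 assessed, the prevalence half-width at 25% is 1.96 × √(0.1875/336) = 4.6 points, well inside the 10-point target.

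**3. Reading B: 84 is the acute pancreatitis cohort.** Patients with EPI: 84 × 0.25 = 21, roughly 10 per arm. The detectable difference under the same assumptions is about 1.3 SD (t-test, 10 per arm: 1.32; normal approximation: 1.25). The expected 95% CI half-width is t(0.975; 18) × √(2/10) = 0.94 SD.

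**4. Which reading the text supports.** The literal wording assigns 42 to each therapeutic arm, which is reading A. The inputs, and the paragraph's place under Phase 1 recruitment, fit reading B. The documents do not settle it.

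**The case against.** The strongest reply is that the figure itself is not wrong: 84 can be reproduced, and 42 per arm may be enough. Both parts stand. This is a mismatch between the rationale and the comparison, not an arithmetic slip. Under reading A, 38 per arm would give close to 80% power for a large effect such as 50% versus 80%.

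A second reply is that detail may sit in Task 1. This also stands in part: an efficacy endpoint could be defined there, so its absence from the supplied text is not charged as an omission, and neither is the missing cohort size. But Task 1 is cited for diagnosis and stratification, not for sample size. An endpoint given there would still leave the written justification resting on prevalence inputs.

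Two further inferences are tempting and should not be drawn.

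- A reader might test the 10-point precision within one arm of 42. The plan does not claim that precision per arm, and the arms cannot estimate prevalence anyway.
- A reader might take the 62% at the top of the abstract's expected range and plan for a much smaller cohort. That range is prevalence at admission, which the abstract expects to fall, so it is not a safe planning value for the number eligible at randomisation.

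**Conclusion.** The point holds as a defect in the sample-size rationale. The only stated basis for 42 per arm answers a different question, in different patients, from the PERT versus placebo comparison, and the reference to statistical power has no value behind it.

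A reader might infer that the trial is underpowered. The documents do not show this: without an endpoint, an effect or a power, adequacy cannot be judged either way. What can be shown is the range left open by the ambiguity, from about 0.65 SD detectable (84 randomised) to about 1.3 SD (84 recruited). These sizes assume two-sided 0.05, 80% power and 25% prevalence. Reading A also takes 10% drop-out; reading B is shown before losses. Per-protocol exclusions would enlarge both. The mismatch itself rests on none of these assumptions.

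It needs correcting because PERT efficacy is a primary objective. A non-significant result would still have an interpretable confidence interval, but readers should know beforehand how wide it is likely to be.

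**What to change.** Rewrite the sample-size paragraph; the rewrite adds no enrolment.

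1. Attach the precision statement (25%, 95% confidence, 10 points) to the acute pancreatitis cohort, and remove it as the justification for the treatment arms.
2. State whether 84 is the number randomised or the cohort. Give the other number that this implies at 25%: about 336 recruited, or about 21 randomised. Do not use the 62% admission figure for planning.
3. For PERT versus placebo, name the efficacy endpoint in the paragraph and state the difference detectable with the number expected in the per-protocol analysis, giving sidedness and power. Otherwise, say that the comparison was not sized for power and will be reported as an estimate with a 95% confidence interval. Give the expected width: about ±0.46 SD or ±22 points at 38 per arm if 84 are randomised, and about ±0.94 SD at 10 per arm if 84 is the cohort.
4. Remove the reference to statistical power unless a value is given.

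The cost is more than wording. The stated justification becomes less favourable, and a primary objective may have to be acknowledged as not formally powered. Naming an endpoint commits the team to it. Stating the implied cohort may show that one centre needs several hundred pancreatitis patients.

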In clinical practice, there is no a universally easy and reliable test for the diagnosis of EPI. Gold standard diagnosis implies direct tests or 72-hour fecal fat quantification. However, their clinical applicability is limited. Valid alternatives such as fecal elastase-1 and C-labeled mixed triglyceride breath test assessing exocrine pancreatic function have gained special interest and wide use for their availability, cost and ease of application. Based on fecal elastase-1, EPI has been reported at 26.5%, 26.1% and 9.4% for a follow-up of <12months, 12-36months and >36months, respectively. Recent evidence suggests an increasing importance of the pancreas-intestinal axis in pancreatic pathology given the central role of the pancreas in controlling metabolism via its exocrine and endocrine pancreatic functions, possibly due to bacterial metabolites as short-chain fatty acids, immune modulation and pancreatic excretion of antimicrobials. Changes in gut microbiota have been more documented for pancreatic cancer and type 1 diabetes mellitus. Recently, [ZhHeLiCaHuLi19] showed that severe acute pancreatitis can also course with gut dysbiosis by decreased Firmicutes and Bacteroidetes and increased Protobacteria. However, the presence and implications of gut dysbiosis associated with acute pancreatitis and EPI following acute pancreatitis increasing risk of gut-derived infection, remains unclear. In recent years, efforts have been dedicated to find early predictors, alone or in association, of severity, organ dysfunction, and development of complications in patients with acute pancreatitis. In fact, our study group has also been dedicating itself to this thematic, having carried out studies and reflections with publications in international and national journals, identifying C-reactive protein (CRP), red cell distribution width (RDW) and RDW to total serum calcium ratio, as main early predictors (at admission of patients and within the first 24 hours of hospitalization) of severity in acute pancreatitis. However, no single biomarker or score demonstrated high accuracy in early prediction of severity or prognosis of acute pancreatitis to be used in clinical practice and, additionally, there are no studies on early predictors in the development of the EPI complication after acute

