#### D.4. Statistical analysis

Using of Statistical Package for the Social Sciences (SPSS) version 25.0 (IL, USA). The statistical significance level will be for a p-value < 0.05. The distribution of data normality will be evaluated by Kolmogorov-Smirnov or Shapiro-Wilk tests. Continuous variables will be expressed as mean and standard deviation or median and interquartile range. Categorical variables will be expressed as frequency and percentage. Univariable analysis will be performed using the Kruskal-Wallis test or Anova test (continuous variables) and Qui-squared test test (categorical variables). The Wilcoxon or Friedman test and the t-Student or Anova test will be used to compare paired data. Cox regression multivariable analysis will be used to determine the independent factors associated with exocrine and endocrine pancreatic insufficiencies. Analysis of PERT efficacy will be performed per-Protocol (PP), excluding loss of follow-up and PERT non-compliance. The temporal evaluation of EPI and PERT response will be evaluated through Kaplan-Meier survival curves. The genome sequences will be grouped in OTU according to their similarity. The alpha taxonomic richness and diversity of stool samples will be expressed in observed species and Shannon index. The composition of fecal microbiota will be expressed in rarefaction curves and comparison of the differences in OTU richness with the t-Welch test. Immunological findings will be expressed by radar charts and representative FACS dot-plots. Additional statistical analysis will be defined a posteriori.

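### Phase 2 states no timing limit or strata for randomising EPI patients and D.4 no covariates for the PERT comparison, so transient and persistent EPI may be pooled at a cost in power and interpretability

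*Combined protocol and SAP*

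**What the plan says.** The entry rule for the randomised phase in D.3 is one line: "Randomization of patients with EPI following acute pancreatitis for PERT vs placebo". The supplied text adds no time window from acute pancreatitis (AP), no requirement that EPI be shown to persist, and no randomisation strata. Phase 1 provides for "stratification of them according to the severity of acute pancreatitis and development of EPI (12-month follow-up"), so the cohort is grouped by severity, but nothing carries that grouping into the allocation. For EPI diagnosis and stratification, Phase 1 refers the reader to a Task 1 that is not in the supplied text. Outcomes are judged at 1 and 6 months after PERT starts.

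D.4 plans a per-protocol efficacy analysis and Kaplan-Meier curves for PERT response. Its Cox model is for factors associated with exocrine and endocrine insufficiency, not for the treatment comparison. No covariate, stratum or analysis by start time is named for PERT v placebo.

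The Abstract says: "With this study we expect to obtain a prevalence of EPI at admission of 25-62%, which should decrease during" follow-up. It also expects alcoholic aetiology, severity and necrosis to be associated with the presence of EPI. Section B lists when to start PERT among the primary objectives, and section C gives the randomised trial the task of settling start timing.

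**The concern.** If EPI found early often clears without treatment and EPI found later does so less often, the randomised group is a mixture. Patients who would recover anyway do so in both arms and contribute nothing to the treatment difference. A null pooled result could then mean that PERT does nothing, or that too few patients had EPI on which it could act, and the planned analysis could not tell these apart. With 42 per arm and no strata, the arms may also differ by chance in their share of early or severe cases. Finally, the plan cannot address when to start PERT if no analysis uses time since AP.

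**Working it through.** **1. The plan's sample size.** D.3 works from "For an estimated prevalence of EPI in the adult population of 25% and a drop-out rate of 10"%, "for a 95% confidence level and 10% sampling error", and concludes that "it will be necessary to include 42 patients in each of the therapeutic arms (PERT vs placebo), making a total of 84 patients". The single-proportion precision formula is n = z²p(1−p)/d²:

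- 1.96² × 0.25 × 0.75 / 0.10² = 72.03
- split over two arms: 36.01, rounded up to 37
- 37 / 0.90 = 41.1, rounded up to 42 per arm, 84 in total

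The figure reproduces, but as precision for a prevalence. It contains no PERT effect, no power and no allowance for recovery. D.4 says "The statistical significance level will be for a p-value < 0.05". Read as two-sided, 42 per arm has 80% power only for a difference of about 29-30 points (control rate 25-50%).

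**2. How much EPI might resolve.** The Literature review states that "EPI has been reported at 26.5%, 26.1% and 9.4% for a follow-up of <12months, 12-36months and >36months", respectively. Assume that the fall from the expected admission prevalence to the figure for under 12 months is all resolution, with no new cases:

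- from 62%: 1 − 26.5/62 = 0.573, about 57%
- from 25%: 26.5% is no lower than 25%, so essentially none

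The documents therefore allow anything from 0 to about 57%.

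**3. Dilution.** Let w be the share of randomised patients with admission EPI and r the share of those that resolves. If the benefit is confined to persistent EPI, and EPI found later is treated as persistent for this sum only, the pooled difference is the true difference × (1 − w·r). For a true difference of 30 points (assumed):

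| w | r | Pooled difference |
|---|---|---|
| any | 0 | 30 |
| 0.5 | 0.573 | 30 × (1 − 0.286) = 21.4 |
| 1.0 | 0.573 | 30 × (1 − 0.573) = 12.8 |

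The documents do not give w. One half is an assumption, and the last row requires every randomised patient to have admission EPI.

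**4. Power.** Assume response of 20% on placebo and 50% on PERT in persistent EPI, and 90% in both arms in self-resolving EPI. With a self-resolving share of 0.286:

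- placebo: 0.286 × 0.9 + 0.714 × 0.2 = 0.400
- PERT: 0.286 × 0.9 + 0.714 × 0.5 = 0.614

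Power = Φ{[Δ − 1.96√(2p̄(1−p̄)/n)] / √[(p₁(1−p₁) + p₂(1−p₂))/n]}. With n = 42, Δ = 0.2142 and p̄ = 0.507, the critical difference is 1.96 × 0.1091 = 0.2138, so power is about 50%. By the same formula, power is 83% with no self-resolving patients and about 24% with a 57% share.

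**5. Chance imbalance.** Suppose 42 of the 84 have early EPI and allocation is an unstratified 42 v 42. The exact hypergeometric probability that the early-EPI share differs between arms by more than 10 points is 28%. If each arm is instead an independent binomial (42, 0.5), it is 33%.

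**6. Bias and recovery of power.** These come from simulation at the step 4 rates, 20,000 trials per scenario. With no PERT effect, the crude test rejects in about 5-6% of trials. With the effect present, a Cochran-Mantel-Haenszel test stratified on EPI type raises power from 59% to 67% at a 25% self-resolving share, and from 31% to 41% at a 50% share. This test knows the true EPI type. Diagnosis timing is only a proxy for it, so the real gain would be smaller.

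**The case against.** The best defence is that the supplied text is incomplete on exactly this point. Task 1 may set the timing of EPI diagnosis, and D.3 treats EPI diagnosis as a sampling point distinct from AP diagnosis. That stands, and the criticism of timing is limited to what is stated. It does not answer D.4, which names neither factor for the efficacy comparison whatever Task 1 says.

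A second defence is that enrolling all EPI after AP is a legitimate pragmatic choice and suits a question about when to start. The first half stands. The second needs an analysis by start time, and none is planned.

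A third is that stratification does not undo dilution. Step 6 bears this out: the gain is partial.

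Four stronger readings are tempting but not supported:

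- A reader might infer that randomisation runs from admission to month 12. The 12 months belong to Phase 1 follow-up. A patient randomised at month 12 would reach the 6-month assessment at month 18, and no section says entry extends that far.
- A reader might infer that spontaneous recovery can systematically mimic a PERT effect. The concurrent placebo arm has the same recovery in expectation, and the simulated false-positive rate stays near nominal. A spurious effect would need chance imbalance, selection through the per-protocol exclusions, or a before-after reading of D.4's paired tests.
- A reader might say that the plan names time since AP and severity as what governs persistence. The Abstract links severity and necrosis to the presence of EPI, and otherwise says only that prevalence should fall.
- A reader might say that severity is ignored altogether. It is used to group the Phase 1 cohort. What is missing is any stated use in allocation or in the PERT comparison.

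**Conclusion.** The point holds as a loss of power and interpretability, not as a systematic bias. As written, Phase 2 and D.4 allow transient and persistent EPI to be pooled, use neither diagnosis timing nor severity in the PERT comparison, and leave a primary objective on start timing without an analysis.

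The size is uncertain. On the documents' prevalence figures the loss ranges from nothing (25% at admission) to a fall from 30 to about 21 points (62% at admission, half of randomised patients with admission EPI). On the assumed response rates, the latter takes power from 83% to about 50%. These results assume no new cases, join an expected admission range to literature prevalences as if they came from one cohort, and use response rates that the documents do not supply. The 28-33% chance of an imbalance above 10 points assumes half of the patients have early EPI and that allocation is unstratified. The change is worth making because it is cheap and because the timing objective cannot otherwise be addressed.

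**What to change.** **In D.3, Phase 2:** stratify the randomisation by timing of EPI diagnosis (index admission v follow-up) and by revised Atlanta severity (mild v moderately severe or severe), with permuted blocks in the four strata. Carry into this section any timing rule that Task 1 contains.

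**In D.4:** adjust the PERT-placebo comparison for both factors. Report the PERT effect by timing of diagnosis, labelled as a supportive and imprecise estimate for the objective on when to start. Do not describe follow-up-diagnosed EPI as persistent EPI: EPI first found at an early visit may still resolve, and on the figures above at least 43% (1 − 0.573) of admission EPI does not.

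**Cost:** a stratified allocation list and two covariates that the study already collects, namely the severity grade from Phase 1 and the date of EPI diagnosis. With four strata in 84 patients some blocks may stay incomplete, and the estimates by timing will be imprecise. Stratification and adjustment recover only part of the power lost to dilution, so the sample size justification should not rely on them to restore it.
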